12.2.1.1 Primary efficacy variable

The primary analysis will compare the time from randomisation to the first occurrence of any event in the composite endpoint of stroke, MI and death. The null hypothesis will be that the risk/hazard of an event on ticagrelor is equal to the corresponding risk/hazard on ASA ie;

 H_0 : HR (ticagrelor divided by ASA) = 1

The alternative hypothesis will be that the HR is greater, or less than 1, ie:

 H_1 : $HR \neq 1$

The hypothesis will be tested at 4.98% two-sided significance level.

The HR and 95% confidence interval will be reported. Kaplan Meier estimates of the cumulative incidence to the first occurrence of any event in the composite endpoint will be calculated and plotted.

The assumption of proportional hazards for the factor for treatment group will be assessed visually using log-cumulative hazard plots. The effect of any departures from proportional hazards will be discussed as part of the presentation of results of the analyses.

Subgroup analysis will be performed to evaluate variation of treatment effect, as well as a test of interaction with treatment for each subgroup variable. The p-values of the subgroup analyses and interaction tests will not be adjusted for multiple comparisons as the tests are exploratory and will be interpreted descriptively. Hazard ratios and 95% confidence intervals will be reported for each subgroup. Relevant subgroups will be examined for e.g. age, sex, race, weight/BMI, diabetes and other medical history characteristics.

12.2.1.2 Secondary efficacy variable included in a hierarchical test sequence

The analysis of the primary composite variable will be repeated for the secondary efficacy variable for the test of ticagrelor against ASA:

Time from randomisation to first occurrence of any ischaemic stroke

The analysis of the primary and this secondary efficacy variable will comprise the confirmatory analysis. In order to address the issue of multiple testing, a hierarchical test sequence will be used.

If the treatment effect on the primary efficacy variable is significant at the 4.98% level, the secondary efficacy variable listed above will be tested in a confirmatory sense. Otherwise it will be tested in an exploratory manner.

12.2.1.3 Other secondary efficacy variables

- 1. Time from randomisation to first occurrence of any of the events which comprise the Net Clinical Outcome
- 2. Time from randomisation to first occurrence of any event of the composite of ischaemic stroke, MI and CV death
- 3. Time from randomisation to first occurrence of all-cause death
- 4. Time from randomisation to first occurrence of CV death
- 5. Time from randomisation to first occurrence of MI
- 6. Severity of stroke and overall disability of patients at the end of study using mRS, see Appendix C

- 7. Time from randomisation to first occurrence of all stroke (including haemorrhagic stroke)
- 8. Time from randomisation to first occurrence of fatal stroke
- 9. Time from randomisation to first occurrence of disabling stroke
- 10. Change from baseline in the score on the NIHSS, see Appendix C
- 11. Health care utilization and utilities assessed by EQ-5D questionnaire

For the time to event variables (1 to 5 and 7 to 9 above), ticagrelor and ASA treatment groups will be compared using the Cox proportional hazards model with a factor for treatment group. Kaplan-Meier estimates of the cumulative incidence of each event will be calculated and plotted and 95% CI for the hazard ratios presented.

The difference between treatment groups in the NIHSS, EQ-5D, hospitalizations and the modified Rankin Score will be analysed descriptively. See Section 6.9 for a description of collection and further analysis of health economic data.

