2.2 Secondary objectives

The first secondary objective of the study is to compare the effects of treatment with ticagrelor vs ASA on:

• Prevention of subsequent ischaemic stroke

Other objectives

Other objectives are to compare the effects of treatment with ticagrelor vs ASA on:

- Net clinical outcome (stroke + MI + death + life threatening bleeding)
- Prevention of composite of ischaemic stroke, MI and CV death
- Prevention of all-cause death, CV death and MI, individually
- Severity of stroke and overall disability of patients using modified Rankin Scale (mRS) (See Appendix C)
- Prevention of all stroke (including haemorrhagic stroke), fatal stroke and disabling stroke, individually

² ASPIRINTM (acetylsalicylic acid) is a trademark of Bayer AG, Germany

- Rate of worsening, ie, progression of the index stroke event by deterioration in clinical symptoms and/or an increase in the score on the National Institute of Health Stroke Scale (NIHSS) (See Appendix C)
- Health care resource and utilities assessed by Euro Quality of Life-5 Dimensions to support health technology assessment and health economic modelling

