All patients contacts that may result in reporting of AE, SAE or endpoint events between planned study visits should be documented as Unscheduled visits in the eCRF. Also if a patient develops any neurological worsening after randomization an unscheduled visit in eCRF should be used to record NIHSS and reporting of potential endpoint event. Patients who prematurely and/or permanently discontinue treatment with study medication but agree to continue in the study, should return for a Premature Treatment Discontinuation Visit (PTDV), which will be done as soon as possible but no later than 15 days after prematurely discontinuing treatment with study medication. After PTDV the patient will, whenever possible, continue attending subsequent study visits according to schedule until study closure on Day 120 after randomisation. All patients should attend the Study Closure Visit 6 in person (if necessary it may be a telephone contact). Patients who refuse to attend scheduled visits will be contacted for assessment of health status or vital status as per agreement, ie, by telephone or by collecting information from publicly available sources. For further details regarding discontinuing patients from study medications see Section 5.8, and for patients who must withdraw from the study, see Section 5.9. One interim analysis will be performed by the DMC following the accrual of 50% of planned primary events (422) adjudicated by the CEC and include both futility and efficacy analyses.

Figure 1 Study flow chart

bd Twice daily; d Day; EoT End of Treatment; od Once daily; R Randomisation; SCV Study closure visit; TIA Transient ischaemic attack

Visits 3 and 4 are telephone contacts. Visit 6 may be a telephone contact, if necessary.

After EoT Visit on Day 90 patients will be treated with Standard of Care therapy of Investigator's choice.

Study Plan Table 1

	Visit 1	Visit 2	Visit 3 TC	Visit 4 TC	PTDV	Visit 5 EoT	Visit 6 SCV ^a
Assessment	Enrolment/ randomisation ^b	Day 7 ± 2 d	Day 30 ± 7 d	Day 60 ± 7 d	≤15 days after last dose ^c	Day 90 ± 7 d	Day 120 ± 7 d
Signed Informed Consent	$\sqrt{}$						
Eligibility criteria	$\sqrt{}$						
Relevant medical and surgical history ^d	$\sqrt{}$						
Demographics	\checkmark						
Vital signs	\checkmark				\checkmark	$\sqrt{}$	
Modified Rankin Score	\checkmark				\checkmark	$\sqrt{}$	
NIHSS ^e	\checkmark				\checkmark	$\sqrt{}$	
ASCOD Classification of Stroke ^f	\checkmark				$\sqrt{}$	$\sqrt{}$	

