Health Economic Assessment ^g	\checkmark	\checkmark			$\sqrt{}$	$\sqrt{}$	
CT/MRI ^h	\checkmark						
ABCD ² Score for TIA patients	\checkmark						
Dispense Study Medication	\checkmark						
Return Study Medication					$\sqrt{}$	$\sqrt{}$	
Compliance/drug accountability					$\sqrt{}$	$\sqrt{}$	
Compliance reminder ⁱ	$\sqrt{(72h)}$		\checkmark	$\sqrt{}$			
Current Medications	$\sqrt{}$	$\sqrt{}$	\checkmark	$\sqrt{}$	$\sqrt{}$	$\sqrt{}$	$\sqrt{}$
AEs, SAEs and Endpoints ^j	\checkmark	$\sqrt{}$	\sqrt{k}	\sqrt{k}	$\sqrt{}$	$\sqrt{}$	\sqrt{k}

If necessary, Visit 6 may be a telephone contact. Randomisation should be done immediately after enrolment.

The Premature Treatment Discontinuation visit (PTDV) is only done for patients who prematurely and permanently stop study medication.

- Relevant existing data from admission to hospital will be reviewed and recorded into the eCRF.
- NIHSS: Will be captured only in patients with stroke at randomisation, and at the time of subsequent suspected stroke event(s) in all patients. NIHSS will also be captured in all randomised patients at PTDV and visit 5.
- ASCOD classification can be done at any time during hospitalisation for both Stroke and TIA patients based on available data generated in clinical practice.
- See section 6.9.1 for details
- As standard of care, documented acute, ischaemic brain lesion by computed tomography (CT) scan or magnetic resonance imaging (MRI) captured within 24 hours of onset of symptoms of index event(s).
- At 72h after randomisation the patient will be reminded of the importance of compliance, either by TC or during hospitalisation. At TC at 30 and 60 days compliance will be asked for and any reported drug stops be recorded in the eCRF.
- SAEs will be recorded from the time of informed consent. AEs of interest and endpoints will be collected from the time of randomisation.
- In case any AE/SAE or endpoint is reported at TC the patient might need to visit site for evaluation at an unscheduled visit.
- Investigators should record Modified Rankin Score (MRS) at baseline based upon the patient's status before the onset of the index event (up to 72 hours).

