Appendix C

Modified Rankin Scale, NIH Stroke Scale, Euro Quality of Life-5 Dimensions and ASCOD

INTRODUCTION

The research activities and adhering scales described in this appendix are Modified Rankin Scale, NIH Stroke Scale, Euro Quality of Life-5 Dimensions, and ASCOD.

DEFINITIONS AND USE

Modified Rankin Scale (mRS): This scale will be used to measure severity of stroke and overall disability of patients. MRS requires a user certificate.

NIH Stroke Scale (NIHSS): Rate of worsening, i.e., progression of the index stroke event assessed by deterioration in clinical symptoms and/or an increase in the score on the NIHSS. NIHSS requires certification every other year.

NB: Note that the intervals shown in the NIH Stroke Scale:

[] Baseline [] 2 hours post treatment [] 24 hours post onse	t of symptoms ±20 minutes [] 7-10 days
[] 3 months [] Other()

are not applicable in the SOCRATES Study (D5134C00001).

Euro Quality of Life-5 Dimensions (EQ-5D): Patients' health related quality of life will be measured using the EQ-5D quality of life questionnaire to support health technology assessment and health economic modelling. The EQ-5D paper form will be filled in by the patients, or a proxy (site personnel or family member) under the supervision of the study staff. EQ-5D will only be administered in countries where an official language version is available. The English version for UK is included in Appendix C. Translations of EQ-5D into local languages have been performed according to a linguistic validation process.

ASCOD (Atherosclerosis, Small-vessel disease, Cardiac pathology, Other causes, **Dissection):** Classification of Stroke (5 categories to grade).

REFERENCES

Amarenco 2013

Bonita 1988

Rankin 1957

Rankin J. Cerebral vascular accidents in patients over the age of 60. Scott Med J 1957;2:200-15.

Van Swieten 1988

MODIFIED RANKIN SCALE (MRS)

Score	Description
0	No symptoms at all

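### The objective asks for a rate of index-stroke worsening, but variable 10 (change from baseline in NIHSS) does not give one

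*Protocol*

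**What the plan says.** - **Objective** (Protocol 2.2, and likewise in the synopsis): "Rate of worsening, ie, progression of the index stroke event by deterioration in clinical symptoms and/or an increase in the score" on the NIHSS.
- **Variable** (12.2.1.3, item 10): "Change from baseline in the score on the NIHSS", with a pointer to Appendix C. The line gives no time point and no criterion for worsening.
- **Method** (12.2.1.3): "The difference between treatment groups in the NIHSS, EQ-5D, hospitalizations and the modified Rankin Score will be analysed descriptively".
- **Appendix C**, to which item 10 points: "Rate of worsening, i.e., progression of the index stroke event assessed by deterioration in clinical symptoms and/or an increase in the score on the NIHSS". It repeats the objective and adds no threshold or window.
- **Scheduled scores** (Table 1 in Section 3.1): NIHSS is ticked at Visit 1, the premature treatment discontinuation visit (PTDV) and Visit 5. The footnote on the randomisation score reads "Will be captured only in patients with stroke at randomisation". The same footnote extends the PTDV and Visit 5 scores to all randomised patients.
- **Unscheduled scores** (3.1): after any neurological worsening, "an unscheduled visit in eCRF should be used to record NIHSS".
- **Adjudication** (6.3): every neurological worsening, however mild, is to be reported as a possible endpoint and reviewed by the adjudication committee. Ischaemic worsening of the index stroke is not separated from a new stroke.
- **Analysis set** (12.1.1): all efficacy variables use the full analysis set (FAS).

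**The concern.** The objective concerns an event: did the index stroke progress, and in how many patients per arm? The variable assigned to it is the size of a score difference. A reader of the study report would look for a proportion worsening and find a summary of change. That summary mixes patients who recovered with patients who deteriorated, and it depends on when the second score was taken. Progression recognised clinically without a higher score would have no place in it.

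The gap is wider than wording because worsening that is not accepted as a stroke may appear nowhere else. Section 6.4.3 treats deterioration in the original territory as disease progression, not as an adverse event, and as an endpoint only if it qualifies as a new stroke. At stake is whether one stated objective gets an answer. The confirmatory conclusions are not affected.

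**Working it through.** The plan gives no rate, standard deviation, sample size or power for the NIHSS variable, so there is no figure to reproduce. The check sets the objective against the variable and the data collection.

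1. **Type of quantity.** The objective needs a numerator (patients who worsened) and a denominator (patients with an index stroke). Item 10 defines neither.

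2. **Coverage.** The objective has two limbs: clinical deterioration, and/or a rise in NIHSS. A change score can address only the second.

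3. **Timing.** Item 10 names no time point. The only scheduled follow-up scores are at PTDV and Visit 5 (Day 90 ± 7). Take an assumed patient who enters at 2, rises by 4 to 6 at an unscheduled visit, and scores 1 at Visit 5. The change to Visit 5 is 1 − 2 = −1. The patient worsened, but the change score shows improvement.

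4. **A mean change does not identify the rate.** All inputs here are assumed. Worsening occurs in a proportion p_A on ASA and 0.8 × p_A on ticagrelor. Worsening adds 4 points, a share f of it is still present at Visit 5, and everyone else improves by 1 point.
   - Mean change in an arm with proportion p: p·w − (1 − p), with w = 4f − (1 − f).
   - Difference between arms: (p_A − 0.8·p_A)(w + 1) = 0.2·p_A × 5f = p_A × f.
   - With p_A = 6% (so 6% vs 4.8% worsening):
     - f = 1: means −0.70 and −0.76, difference 0.06.
     - f = 0.5: means −0.85 and −0.88, difference 0.03.
     - f = 0: means −1.00 and −1.00, difference 0.
   - For p_A from 4% to 8% the difference is 0.04 to 0.08, 0.02 to 0.04, and 0 respectively.

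   The proportions worsening are the same in all three cases. The mean change depends on how much worsening persists, so the rate cannot be read from it.

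5. **Population.** The FAS includes TIA patients. They have a Visit 5 score but no score at randomisation, so no change can be formed. Section 4.1 defines TIA by complete resolution of the deficit, so they also have no index stroke to progress. The right denominator is index-stroke patients, and the protocol does not say so.

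6. **Data available for a rate.** Baseline scores in stroke patients, unscheduled scores at worsening (3.1), scores at PTDV and Visit 5, adjudication of every worsening (6.3) and adjudicated deaths (6.3.1) are all collected already.

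**The case against.** The strongest reply is that item 10 is descriptive, non-confirmatory and points to Appendix C, where the rate wording appears. A table of change from baseline can include the proportion with an increase, and such derivations commonly belong in the statistical analysis plan, which is not shown. This stands in part: missing detail alone would be no finding. But the protocol names a variable, and that variable differs in kind from the objective. Appendix C only restates the objective. Even a proportion with an increase at Visit 5 would leave out resolved worsening and the clinical limb.

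Several stronger readings are tempting, and the document does not support them.

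- **That the trial misses transient worsening.** It does not. Worsening is scored at an unscheduled visit and adjudicated, and rapid worsening attributed to new infarction meets the ischaemic stroke criteria in 6.3.3. It can therefore count in the primary endpoint, the first secondary variable and all stroke. Only a change score taken at PTDV or Visit 5 would fail to show it.
- **That deaths are omitted, or that the result can point the wrong way.** The protocol is silent on deaths in this summary. Deaths are analysed as all-cause death, CV death and fatal stroke, and the modified Rankin Scale has a category for death.
- **That the variable mainly measures recovery at Day 90.** Entry NIHSS of 5 or less limits improvement to 5 points, but no time point is stated and no recovery data are given.
- **That the change score costs power.** No test is planned. If worseners shift by one fixed amount and everyone else by another, mean change is a linear function of the proportion worsening and carries the same information. A loss appears only once extra spread is assumed, and the document gives no basis for choosing it.
- **That TIA patients' missing baseline loses needed information.** The objective concerns the index stroke, so the only gap is the unstated restriction of the population.

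**Conclusion.** The point holds as a mismatch between objective and variable. Item 10 does not yield a rate of worsening and does not cover clinical deterioration. If summarised at the scheduled follow-up scores, it would not show worsening that has resolved. The population should be index-stroke patients, not the whole FAS.

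The importance is low. The variable is descriptive, lies outside the hierarchical test sequence and affects neither the primary result nor the error rate. No numerical effect can be taken from the document; the group figures above illustrate the mechanism under assumed inputs only. The Day 90 timing is inferred from the visit schedule, since item 10 does not state it.

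**What to change.** In Section 12.2.1.3, replace item 10 with the number and proportion, by arm, of index-stroke patients with worsening through Visit 5. Count a patient as worsened if any of the following occurs:

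- an NIHSS above baseline at any unscheduled visit, PTDV or Visit 5;
- neurological worsening reported and adjudicated under Section 6.3;
- death from stroke.

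Keep change from baseline as a supporting descriptive table, limited to index-stroke patients who have a score. Setting the definition before unblinding avoids a post hoc choice.

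The cost is a change of wording and one table from data already collected, with no new assessment. There are two downsides. Unscheduled scores depend on sites reporting worsening. The count will also overlap partly with the stroke endpoints, because ischaemic worsening is not separated from new stroke; a note under the table should say so.

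### Overall disability by mRS is a stated between-arm objective, but Section 12.2.1.3 gives it a descriptive analysis with no named effect measure or interval; one sentence would improve this

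*Protocol*

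**What the plan says.** Section 2.2 opens its list of further objectives with "Other objectives are to compare the effects of treatment with ticagrelor vs ASA on", and one item is "Severity of stroke and overall disability of patients using modified Rankin Scale (mRS").

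Section 12.2.1.3 carries this forward as variable 6: "Severity of stroke and overall disability of patients at the end of study using mRS, see Appendix C". It then divides its eleven variables into two groups:

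- Variables 1 to 5 and 7 to 9: "For the time to event variables (1 to 5 and 7 to 9 above), ticagrelor and ASA treatment groups will be compared using the Cox" model, with Kaplan-Meier curves and a 95% interval for each hazard ratio. Variable 9 is "Time from randomisation to first occurrence of disabling stroke".
- The scale and resource measures: "The difference between treatment groups in the NIHSS, EQ-5D, hospitalizations and the modified Rankin Score will be analysed descriptively".

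The study plan (Section 3.1, Table 1) schedules mRS at Visit 1, at the premature treatment discontinuation visit and at Visit 5 (Day 90), but not at Visit 6 (Day 120). A footnote defines the first value: "Investigators should record Modified Rankin Score (MRS) at baseline based upon the patient's status before the onset of the index event (up to 72 hours"). Appendix C gives the scale as 0 to 6, with death scored 6.

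**The concern.** The objective is comparative, but the stated analysis names nothing that would express the comparison: no odds ratio, no difference in proportions and no interval. The neighbouring variables, and even the exploratory subgroups in Section 12.2.1.1, are each promised an estimate with a 95% interval.

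What is at stake is modest but real. Overall disability at Day 90 puts benefit, harm and death on one scale, which is useful for a drug whose main acknowledged risk is bleeding (Section 1.4). If only summaries by arm are reported, the reader cannot tell how precisely the trial has answered this objective. An effect measure chosen after the data are seen is also less convincing than one fixed beforehand.

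**Working it through.** **1. Is the method left open?** Section 12.2.1.3 assigns a method to mRS, so this is a stated choice and not a silence. Sections 12.2.1 and 12.2.1.1 also use the word *descriptively*, but for intervals, p-values and tests that are already named and are then to be *interpreted* that way. In Section 12.2.1.3 the mRS difference is to be *analysed* that way, and no estimate is named.

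**2. Does disabling stroke fill the gap?** Partly. Variable 9 has a hazard ratio with an interval. It counts only new stroke events, and Section 12.2.4 makes all deaths censoring events for endpoints that do not include death. It does not measure overall functional status.

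**3. Which assessment is meant?** Variable 6 places mRS at the end of the study. Section 5.8.3.2 puts that end at 120 days, yet the last scheduled mRS is at Visit 5, Day 90. Visit 5 is the only workable reading.

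**4. What precision would a named measure have?** The protocol gives no figure for mRS, so there is none to reproduce. Its 88.7% power concerns the primary endpoint and does not bear on this point. Inputs: N = 13600, allocated 1:1 (Section 12.3), mRS assumed complete, and an *assumed* Day-90 distribution, because the protocol gives none.

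For a common odds ratio, the information is V = (N/12)(1 − Σp³), the standard error of the log odds ratio is 1/√V, and the 95% interval is the estimate times or divided by exp(1.96/√V).

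- Assumed mRS 0 to 6 = 45/30/12/6/4/1/2%: Σp³ = 0.120; V = 1133.3 × 0.880 = 997; SE = 0.0317; factor = exp(0.062) = 1.064.
- Range: 1 − Σp³ = 0.95 gives V = 1077 and factor 1.062; 1 − Σp³ = 0.70 gives V = 793 and factor 1.072.

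The interval is therefore about times or divided by 1.06 to 1.07, and it depends little on the assumed distribution. If mRS were cut in two, the half-width for a risk difference would be 1.96√(2p(1−p)/6800): about 1.0 percentage point at p = 10% and 1.7 points at p = 50%.

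**5. Can power be claimed?** An odds ratio of 0.90 would give Φ(0.1054/0.0317 − 1.96) = 91% under the first distribution, but the design does not support an effect of that size.

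- 844 events in 13600 patients is 6.2% overall. With a hazard ratio of 0.8 this splits into about 6.9% on ASA and 5.5% on ticagrelor, a gap of 1.3 points.
- With 25% at mRS 2 or more on ASA, an odds ratio of 0.90 needs 0.9 × 0.333 = 0.300 odds, or 23.1%. That is a drop of 1.9 points, more than the whole assumed reduction in primary events.
- If every avoided event crossed that cut: 25% falls to 23.7%, the odds ratio is 0.93, and power is Φ(0.0726/0.0317 − 1.96) ≈ 63%.
- If half did: the odds ratio is about 0.965 and power about 20%.

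**The case against.** The strongest reply is that nothing here is wrong. Only the primary composite and ischaemic stroke are confirmatory (Sections 12.2.1 and 12.2.1.2), and Section 3.2.3 does not name mRS among the other secondary endpoints. Giving event variables a Cox model and scale measures a descriptive treatment is coherent in an event-driven trial. An objective to compare does not oblige a model: the health-economic objective stands in the same list and is also reported descriptively (Section 6.9.1). The sentence does refer to the difference between groups, and a statistical analysis plan, not shown here, could attach an interval to it. All of this stands, and it makes the point an improvement and not an error.

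It does not remove the point. The protocol states a method for mRS that is less informative than the one it gives the variables beside it, and it does not require anything more.

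Stronger readings are tempting, and the documents do not support them:

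- *That the trial yields no estimate or interval for disability.* Disabling stroke has both, and EQ-5D and NIHSS also bear on function. The gap is confined to mRS.
- *That the protocol forbids an interval, or limits mRS to percentages by arm.* It says neither.
- *That the trial is well powered for a shift in mRS.* Step 5 shows that this rests on an effect larger than the design implies.
- *That the baseline mRS allows a change score.* It records status before the index event, so it can serve as a covariate but not as a post-stroke starting point.

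**Conclusion.** The point holds as a cheap, optional improvement: a comparative mRS objective is paired with an analysis that names no effect measure and no interval. No confirmatory conclusion, sample size or error rate is affected.

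The gain is an estimate with known precision, about times or divided by 1.06 to 1.07 for a common odds ratio. This rests on assumed mRS distributions, on 13600 patients with complete Visit 5 scores and on proportional odds. No power claim should be attached to it.

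**What to change.** In Section 12.2.1.3, take mRS out of the descriptive sentence and add:

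> Visit 5 mRS (0–6, death = 6) will be compared in the FAS with a proportional-odds model with treatment, pre-index mRS and index event type (stroke/TIA). The common odds ratio and 95% CI will be reported with the full distribution by arm, as an exploratory analysis outside the confirmatory sequence. If proportional odds is not tenable, the Mann-Whitney probability with 95% CI will be given.

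Change variable 6 to name Visit 5, which removes the mismatch with the study plan.

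The cost is one sentence and one model on data already collected, with no change to patients, visits or alpha. The drawback is that the proportional-odds assumption must be checked, which is why the fallback is written in. The change should be made before unblinding.
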